In summary, throughout the implementation of these and other studies, we have substantial experience conducting large-scale and complex randomized clinical trials in perinatal health and iron status among pregnant women in Tanzania. Of particular importance to the current proposal is the demonstration that we can enroll large numbers of pregnant women into large-scale clinical trials, and achieve high rates of follow-up and adherence after fully informed consent. Our findings highlight the burden of clinical complications associated with iron deficiency and malaria and provide support to the importance of examining the effect of the safety and efficacy of iron supplementation in the context of high malarial burden, and examining immunological and clinical outcomes related to malaria in pregnancy.

Research Design and Methods

Eligibility criteria: Participants will be recruited from pregnant women presenting to a large prenatal care clinic in Dar es Salaam, Tanzania. More than 90% of women present for their first prenatal care visit after the 12th week of gestation. Eligible participants will be pregnant women at or before 27 weeks of gestation, who are primigravida or secundigravidae, not anemic (defined as Hb<8.5 g/dL) or iron deficient (defined as serum ferritin <12 μ g/L), HIV-uninfected, and intend to stay in Dar es Salaam until delivery and for at least six weeks thereafter. Women with high iron stores at baseline (i.e., serum ferritin >200 μ g/L) will be excluded. HIV-infected women will be referred for standard of care services, including provision of antiretroviral treatment, as needed. The recruitment process will be completed within one week, such that randomization will be completed at the latest by 20 weeks of gestation.

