Laboratory Investigations: A peripheral venous blood sample of 10 ml will be taken from all women at screening, 20 weeks, 30 weeks, delivery, and 6 weeks post-partum. At screening, blood will be tested for a complete blood count and serum ferritin. Following randomization, the following additional assessments will be performed: ABO blood typing as part of standard prenatal care, a sickling test, a blood smear for malaria parasitemia, and c-reactive protein. Malaria parasitemia during pregnancy will be further assessed before ingestion of SP intermittent preventive therapy at 20 and 30 weeks of gestation. At delivery, the following laboratory assessments will be performed in mothers: serum ferritin, c-reactive protein, a complete blood count, and malaria parasitemia. A cord blood specimen and a placental blood specimen from drained retroplacental blood will also be collected at delivery. At the 6 week post-partum visit, malaria parsitemia will be assessed in mothers and a 1 ml specimen will be drawn from the infants through venipuncture for a peripheral blood smear for malaria and a complete blood count. If venipuncture is unsuccessful, however, the heel stick method will be used as an alternative.

Peripheral thick blood smears will be stained with Giemsa and then examined for parasites. Parasite species and density will be recorded. The presence or absence of asexual forms of parasites will be recorded, and the density of such stages will be recorded. Slides will be examined without knowledge of clinical malaria status. In addition, qualitative and quantitative PCR for malaria will be performed at delivery for mothers and at 6 weeks post partum for infants.

After delivery, the placenta will be brought to the laboratory in a sealed plastic bucket containing 500 ml normal saline. A 1 cm3 biopsy will be taken from the maternal side of the placenta

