approximately one fourth of the distance from the center to the edge of the placenta [154]. The specimens will be fixed in 10% neutral buffered formalin and processed for routine paraffin embedding. Paraffin sections ($5 \mu m$ thick) will be stained with haematoxylin and eosin (H&E), Giemsa's stain, and the periodic acid-Schiff technique. Sections will be examined by light microscopy and under polarized light for the presence of malaria pigment and parasitized erythrocytes. The presence of parasites in maternal erythrocytes in intervillous spaces and fetal erythrocytes in fetal stem vessels will be assessed, and, when present, the percentage of parasitized erythrocytes will be estimated. Malaria pigment will be assessed semi-quantitatively (0 = absent; 1 = mild; 2 = abundant) in maternal and fetal parts of the placenta.

Routine examination of urine and stool (i.e. macroscopic and microscopic assessment including presence and burden of parasites) will be done at baseline. On a subset of 300 individuals, iron markers will be measured at randomization and delivery to assess patients' adherence with the use of the regimen and to ascertain the impact of iron supplementation on these indicators. Retinol binding protein and zinc will be measured in order to examine potential interactions between iron and vitamin A and zinc. An extra 5 ml of blood will be drawn from participants in the sub-sampe for these tests. **The above-mentioned laboratory tests will be performed at the Department of Pathology at MUHAS, Muhimbili-Harvard Laboratory in Dar es Salaam**. All laboratory staff, including the pathologist who reads the placental histopathology slides, will be blinded to the mother's randomization group and to any treatments for malaria.

Hemoglobin: Hemoglobin will be measured as part of a complete blood count, measured using a CBC5 Coulter Counter (Coulter Corp. Miami, FL). Sickle cell anemia will be diagnosed using a hemoglobin electrophoresis test.

Serum Ferritin: Ferritin will be measured by a particle-enhanced immunoturbidimetric assay using the Hitachi 917 analyzer (Roche Diagnostics, Indianapolis, IN) and Kamiya Biomedical reagents (Seattle, WA). The reference range for serum ferritin is 15 to 200 mcg/L for women.

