Birth Weight: The difference between mean birth weights in the iron and placebo arms will be calculated, and the statistical significance of any observed difference will be assessed by a two-sample t-test and non-parametrically by a Wilcoxon rank-sum test. A linear regression model will be used to adjust for residual treatment imbalances by risk factors, and to evaluate effect modification by these risk factors, using the methods for multivariate modeling described above.

Analysis of Secondary Endpoints

Low Birth Weight (<2500 g): Analyses of the effects of iron supplements on low birth weight will parallel those outlined above for placental malaria infection, also a binary endpoint.

Maternal anemia (Hb < 11.0 g/dL) and Maternal malaria infection: These binary secondary endpoints, as noted in the Definition of Endpoints section, will be analyzed in a similar fashion as the primary endpoints as described above, although only women without these conditions at baseline will contribute to these analyses.

Analysis of Adherence and Iron Status Biomarkers: Pill counts will be undertaken at monthly clinic visits. Serum concentrations of ferritin will be assessed on all subjects at baseline and among a subset of 300 women at delivery. Increased intake of iron is usually paralleled by increases in serum ferritin values, and concentrations of serum ferritin and pill counts will be compared between the active treatment and placebo arms as proxy indicators for adherence with the supplements. The analysis will be based on a regression model for the change from baseline to delivery and supplemented by Wilcoxon rank-sum tests. Median changes (and associated order-statistic-based 95% CI's) will be summarized by treatment arm. The effect of iron supplementation on serum transferrin receptor, hepcidin, and C-reactive protein will be also examined, following a similar approach.

Statistical Power Calculations

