Power for the primary aims, placental malaria infection and density, maternal hemoglobin levels, and birth weight, have been calculated based on a nominal Type I error rate (alpha) of 0.05, and a 10% sample size adjustment for loss-to-follow-up and fetal loss. Power is based on a 2-sided test of proportions, based on a Z-statistic using the asymptotic variances of the observed proportions. The table below displays the power of the study to detect treatment effects on placental malaria infection. The assumed placebo arm rate of 20-30% is supported by studies reviewed above [37, 39]. Displayed is the power (for treatment effects expressed as % reductions) based on a 2-sided test for comparison of proportions, total enrolled n=1500, with a 10% sample size adjustment to account for loss to follow-up and fetal loss.

Statistical Power for Incidence of Placental Malaria							
Incidence in Placebo Arm	Effect of Intervention on the Incidence						
	HR=0.75	HR=0.70	HR=0.65	HR=0.60			
20%	48%	65%	80%	90%			
25%	57%	74%	87%	95%			
30%	64%	80%	92%	98%			

The study will have good power to detect a 35% effect size, for placental malaria rates as low as 20% in the placebo arm. If the placental malaria rates are larger (25% or 30%), the study will have good power to detect a 30% effect size and excellent power to detect a 40% effect size.

Continuous Variables: The table below displays the power of the study to detect treatment effects on continuous variables, including placental malaria density, maternal hemoglobin concentration, and birth weight. Displayed is the power (for treatment effects expressed as percent changes in effect size) based on a 2-sided test for comparison of proportions, total enrolled n=1500, with a 10% sample size adjustment to account for loss to follow-up.

Placental malaria density: The table below displays the power of the study to detect treatment effects on placental malaria density. The assumed mean placental malaria density in the placebo arm of 9,000 parasites/ μ L is supported by studies reviewed above [156]. The study will have good power to detect an effect size of 8.5%, and excellent power to detect a 10-20% change, based on a 2-sided test for comparison of proportions, total enrolled n=1500, with a 10% sample size adjustment to account for loss to follow-up and fetal loss. The study will have good power to detect an 8.5% effect size, and excellent power to detect an effect size of 10% or greater.

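### Iron-marker analysis by change from baseline, with no baseline covariate or log scale named, is valid but loses precision, mainly for C-reactive protein and hepcidin

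*Protocol*

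**What the plan says.** All places are in the protocol.

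- **Model.** Under Analysis of Adherence and Iron Status Biomarkers, for ferritin: "The analysis will be based on a regression model for the change from baseline to delivery and supplemented by Wilcoxon rank-sum tests".
- **Summary.** Same paragraph: "Median changes (and associated order-statistic-based 95% CI's) will be summarized by treatment arm".
- **Other markers.** Same paragraph: "The effect of iron supplementation on serum transferrin receptor, hepcidin, and C-reactive protein will be also examined, following a similar approach".
- **Number of women.** That paragraph says "Serum concentrations of ferritin will be assessed on all subjects at baseline and among a subset of 300 women at delivery". Laboratory Investigations says "At delivery, the following laboratory assessments will be performed in mothers: serum ferritin, c-reactive protein, a complete blood count, and malaria parasitemia", with no subset, and later says "On a subset of 300 individuals, iron markers will be measured at randomization and delivery". In the laboratory schedule the asterisk for the 300-woman subset marks hepcidin, retinol binding protein, zinc and transferrin receptor, but not ferritin or CRP.
- **Entry range of ferritin.** The eligibility criteria exclude values below 12 µg/L, and also exclude this group: "Women with high iron stores at baseline (i.e., serum ferritin >200" µg/L.

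No scale, transformation or baseline covariate is named for the biomarker regression. The paragraph does not say whether the Wilcoxon test ranks changes or delivery values. In the Hemoglobin paragraph of the same analysis section, change is a within-woman difference, and both the t-test and the Wilcoxon test are applied to it. Arithmetic change is therefore the natural reading here too.

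**The concern.** Two separate features cost precision.

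1. **Change score without baseline.** Subtracting baseline gives it a fixed weight of one. When the correlation between baseline and delivery is moderate, this adds baseline noise to the outcome. Using baseline as a covariate avoids that.
2. **Arithmetic scale.** Entry ferritin may span 12 to 200 µg/L, a 17-fold range (200/12 = 16.7), and delivery values have no cap. CRP is measured by an assay sensitive to 0.03 mg/L, with a reference limit of 5 mg/L and assay variability quoted up to 13.38 mg/L. The plan's choice of median changes suggests that skewness is expected. On such data a woman moving from 180 to 150 µg/L weighs more than one moving from 15 to 25 µg/L.

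The medians are given by arm, so they are not a between-arm effect estimate. The one between-arm estimate the paragraph provides is the regression coefficient, which is the part sensitive to high values.

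Ferritin is the trial's biochemical check on adherence, and the markers are also meant to show what iron did to iron status. A weak analysis could give a null result that is misread as poor adherence or as no biological effect.

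**Working it through.** **The plan's own figures.** The protocol gives no power, SD, correlation or effect for these markers, so there is nothing of its own to reproduce. Its power section uses "a nominal Type I error rate (alpha) of 0.05, and a 10% sample size adjustment for loss-to-follow-up and fetal loss" for the primary aims. Applied to 1500 women this gives 1500 × 0.9 / 2 = 675 per arm. For a 5% change in placental parasite density, 450 / (5000 × √(2/675)) = 1.65 and Φ(1.65 − 1.96) = 38%, as the protocol states. The same convention for the subset gives 300 × 0.9 / 2 = 135 per arm. Equal allocation and 10% loss in the subset are assumptions.

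**Assumed inputs.** Data are lognormal.
- Ferritin-like: log SD 0.7, baseline-delivery correlation ρ = 0.5, ratio of geometric means 1.22, entry cut to 12–200 µg/L.
- CRP-like: log SD 1.2, ρ = 0.3, ratio 1.42.

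**Log scale, closed form.** Analysis of covariance has SE = s√(1 − ρ²)√(2/n), and power is Φ(ln(ratio)/SE − 1.96).
- Ferritin-like: SE = 0.7 × 0.866 × 0.1217 = 0.0738; 0.1989/0.0738 = 2.70; power 77%.
- CRP-like: SE = 1.2 × 0.954 × 0.1217 = 0.1393; 0.3507/0.1393 = 2.52; power 71%.

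**Where the loss comes from.**
- Change score against baseline adjustment, same scale and equal SDs: efficiency (1 − ρ²)/(2(1 − ρ)) = (1 + ρ)/2, which is 0.75 at ρ = 0.5 and 0.65 at ρ = 0.3.
- Arithmetic against log scale for lognormal data, large samples: s²/(exp(s²) − 1), which is 0.77 at s = 0.7, 0.58 at 1.0 and 0.45 at 1.2.

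**Simulation, 135 per arm, two-sided 5%.**

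| Analysis | Ferritin-like | CRP-like |
|---|---|---|
| Regression on arithmetic change | 58% | 29% |
| Wilcoxon on arithmetic change | 61% | 45% |
| Arithmetic scale, baseline as covariate | 64% | 43% |
| Log scale, log baseline as covariate | 76% | 71% |

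The first row also depends on how far the placebo median moves by delivery. In a rerun with the same inputs (2000 trials per cell, about ±2 points), moving from a 30% fall to no fall gave 46–61% for ferritin-like and 22–31% for CRP-like data. Log-scale analysis of covariance stayed at 75–77% and 70–72%.

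**Where the loss is small or has another cause.**
- *Large effect* (ratio 1.6, 150 per arm, ρ = 0.5): ferritin-like 97–100% for arithmetic-change regression against 100%. CRP/hepcidin-like (log SD 1.0) 76–88%, with Wilcoxon on change 94–98%, against 100%.
- *Transferrin-receptor-like* (log SD 0.3, 150 per arm, effect set for about 80%): arithmetic change 40–53%, arithmetic scale with baseline covariate 75–80%, log scale 78–82%. Almost all of the loss is the missing baseline term.
- *All women measured* (675 per arm, same ratios): ferritin-like about 100% for every method. CRP-like 86% for arithmetic-change regression and 99% for Wilcoxon on change, against 100%. The rerun gave 71–88% for the regression across the same range of placebo movement.
- *Type I error*: 4–6% for every method.

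**The case against.** The strongest reply is that the protocol does not say arithmetic change, does not rule out a baseline covariate, and may leave both to a statistical analysis plan that is not shown. That stands as a limit on the point, which is therefore conditional. It does not remove it: the protocol names a specific outcome, change from baseline, and its Hemoglobin paragraph shows what change means there.

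Second, rank tests and medians with order-statistic intervals already protect against extremes. This is partly right, since those summaries are robust. They do not supply an efficient between-arm estimate, and the regression coefficient remains exposed. The Wilcoxon test may also be meant for delivery values. In the CRP-like setting that would give about 68% against 73% for the log-scale analysis in the same run, so on that reading most of the loss for that test goes.

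Third, the simulation is lognormal with a multiplicative effect, which favours the log-scale model by construction. That is fair. The figures illustrate size under stated assumptions and do not estimate this trial's power.

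Fourth, a ratio of geometric means is a different effect measure from a difference in µg/L. That is also fair, and is a real though small cost.

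A reader might infer that the plan throws away up to half the power of the biomarker subset. The documents do not support that as a general statement. It rests on assumed SDs, correlations and modest effects; part of it comes from the missing baseline term and not from skewness; and the 300-woman basis is contradicted for ferritin and CRP.

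**Conclusion.** The point holds in conditional form. If the regression is run on arithmetic change without a baseline term, it is a valid but inefficient analysis of all four markers. Baseline adjustment matters for each of them. The log scale matters mainly for CRP and hepcidin, less for ferritin, and little for a marker with a spread like that assumed for transferrin receptor.

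Illustrative size, with 135 per arm and modest effects: about 58% against 76% power (ferritin-like) and 29% against 71% (CRP-like). These rest on assumed lognormal data, log SDs, correlations and effects, none of which the protocol gives. For a large ferritin effect the loss nearly vanishes. If ferritin and CRP are measured in all women at delivery, it vanishes for ferritin and shrinks for CRP. Hepcidin and transferrin receptor stay in the 300-woman subset under the laboratory schedule.

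A reader might also infer that the trial's main conclusions or error rates are at risk. They are not: type I error is preserved, and these markers are not primary endpoints. The change is worth making because it is cheap and uses data already planned.

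**What to change.** In the biomarker paragraph, or in the statistical analysis plan, state that each marker is analysed by regressing the log delivery value on arm with the log baseline value as covariate. Report the ratio of geometric means with its 95% CI. Keep median changes as description and the rank tests as support, and say whether the rank tests use changes or delivery values.

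Reconcile the number of women with ferritin and CRP at delivery: the Adherence and biomarker-analysis paragraphs limit delivery ferritin to 300, while Laboratory Investigations and the laboratory schedule show ferritin and CRP for all mothers.

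The cost is a sentence or two of text and no new data. The effect is then read as a ratio and not as an absolute change, and a rule is needed for values below the assay limit (0.03 mg/L for CRP) before taking logs.

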In Tanzania, iron deficiency is also recognized as a severe public health problem. According to the National Bureau of Statistics Tanzania Demographic and Health Survey 2004–05 and the WHO Global Database on Anemia, 58.2% (54.0-62.3%) of pregnant women and 47.2% (45.8-48.7%) of non-pregnant women (15-49 yrs) are anemic (Hb < 11 g/dL) in Tanzania [1, 33]. Anemia during pregnancy has been found to be a significant public health burden in both rural and urban settings of Tanzania. An estimated 97,000 disability adjusted life years are lost due to iron deficiency anemia annually in the country [19].

Burden of Malaria and its Complications

An estimated 350 to 500 million cases of clinical malaria occur annually worldwide, resulting in more than one million deaths. The majority of the global burden of malaria resides in sub-Saharan Africa, where 10% of the world's population accounts for approximately 60% of clinical cases and 90% of deaths [34-36]. Malaria in pregnancy is a major public health problem in sub-Saharan Africa. An estimated 25 million women become pregnant in malaria-endemic areas in Africa, leading to 200,000 infant deaths each year [37]. In particular, *P. falciparum* is more frequent and of higher parasite density in pregnant than non-pregnant women [38], and is associated with increased risks of maternal anemia prematurity and low birth weight.

In Africa, the prevalence of maternal malaria and placental malaria are high. In a recent review of 20 studies from eight African countries, the median prevalence of maternal malaria infection (defined as peripheral or placental infection) in all gravidae was 27.8% [37]. A review by Guyatt produced a similar estimate of 26% for placental malaria (range 5–52%) [39]. Prevalence of malaria infection has been found to be higher among primigravida [40-43]. In a study from Kenya, among primigravida, 23% had peripheral malaria, 22% had placental malaria based on smears, and 64% had histological evidence of placental malaria. The corresponding numbers for secundigravidae were 18%, 14% and 54% [44]. In the same study, histologic malaria was associated with significantly higher risks of anemia and low birth weight.

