Ascertainment of Gestational Age: In order to more accurately determine gestational age, women may undergo ultrasonography at baseline. Measurement of the fetal biparietal diameter will be used to determine gestational age. The ultrasound will be carried out by an obstetrician trained by an experienced ultrasound specialist at each of the two proposed clinics. When performed in pregnant women up to 18 weeks of gestation, the accuracy of ultrasound in determining gestational age is approximately plus or minus 7 days. Accuracy should have similar variability in pregnant women between 18 and 20 weeks. Verification of ultrasound findings will be performed by an experienced ultrasonographer in a subset of 10% of pregnant women during the first six months of enrolment, as a measure of quality assurance and quality control.

Study Population Characteristics: Recruitment of women for the proposed study will be conducted at the same clinics where we have enrolled cohorts of pregnant women in other randomized trials. In our experience, the median gestation age at enrollment was 21.4 (mean=20.9, SD=3.6)); approximately two percent of women presented at less than 12 weeks gestation, while close to 50% were at 12 to19 weeks gestation. Of all enrolled women, 94.5% of women delivered at a study hospital, while 5.5% delivered at home. More than 50% of women were primigravida or secundigravidae: a quarter of the women were primigravida, another quarter secundigravidae, and the rest were multigravidae. Acceptance of voluntary counseling and testing for HIV has been more than 95%.

A Food Frequency Questionnaire was used to assess dietary intake among 8,265 HIV-uninfected pregnant women in the PeriNatal study in Dar es Salaam, Tanzania in 2005. At baseline assessment, pregnant women consumed an average of 13.4 (s.d. 7) milligrams of iron daily, with a median of 12.0 grams, and an interquartile range of 9.6 to 14.9 grams. An estimated 12.7% of iron intake (1.7 mg) was heme iron, derived from meat, fish, and poultry food sources, with 87.3% of daily iron intake from non-heme sources, on average. Total energy intake was 2,398 calories daily, on average (median: 2,295; IQR: 1843.7). Average consumption of vitamin C was 161.4 milligrams (s.d. 103.5 mg); estimated intake of phytates and zinc were 2263.6 (s.d. 889.2) and 9.6 (s.d. 3.6) milligrams, respectively [145].

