
• Accrual: Recruitment will take place at a large prenatal clinic. This will require a good organizational and supervision system. We have used a system of similar complexity to screen approximately 40,000 women every year as part of previous and ongoing perinatal/child health trials.

• Retention: A major limitation in large trials is the operational difficulty in following up subjects for long periods of time. We have experience with studies of similar design in Tanzania in which we instituted a package of non-coercive incentives for patients to continue coming for follow-up. As a result of these procedures we are able to achieve follow-up rates of 85-95%.

• Bias: The potential for observation bias exists in intervention studies such as this one if the researchers are aware of the experimental regimen to which a subject has been assigned. To avoid the researchers' assessment from being influenced by the regimen received, this will be a doubleblind study such that during the study neither the investigators nor the study subjects will know what each regimen contains.

• Adherence: We recognize that non-adherence decreases the statistical power of a study to detect any true effect of the regimens. Our power calculations show adequate power even after realistic amount of non-adherence. In addition, we intend to perform statistical analyses to adjust for non-adherence. During the implementation of the study, we will monitor adherence by questioning the subjects, by pill count, and by measurement of plasma serum ferritin levels in a sub-sample of subjects. We will attempt to maximize adherence of the study subjects by providing counseling and allowing the patients adequate time to think through the issues during the recruitment phase, thus eventually selecting a study population that is interested and reliable. Furthermore, we believe that the set of incentives we will provide, as discussed above, will reduce non-adherence.

• Capacity: Research in many developing countries is limited by the lack of well-equipped laboratories and well-trained research staff. Tanzania is one of the exceptions since a number of research projects with substantial laboratory and field research components have been implemented. Several of these studies have been carried out as collaborative efforts between Harvard School of Public Health and Muhimbili University of Health and Allied Sciences.

Summary

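### The placental-malaria power table does not follow from its stated test and sample size, and the claim that power holds after non-adherence has no stated basis; the continuous-outcome table allows for none

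*Protocol*

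**What the plan says.** Under Statistical Power Calculations, power for the primary aims is said to "have been calculated based on a nominal Type I error rate (alpha) of 0.05". For placental malaria: "Power is based on a 2-sided test of proportions, based on a Z-statistic using the asymptotic variances of the observed proportions". The sample size is "total enrolled n=1500, with a 10% sample size adjustment to account for loss to follow-up and fetal loss", and effects are described as percentage reductions from placebo rates of 20, 25 and 30%. The table's columns are nevertheless headed HR = 0.75, 0.70, 0.65 and 0.60. The text concludes: "The study will have good power to detect a 35% effect size, for placental malaria rates as low as 20% in the placebo arm". It adds that at 25% or 30% there is good power for a 30% effect and excellent power for a 40% effect.

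A second table covers placental parasite density, hemoglobin and birth weight, again with a 10% adjustment.

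Under Limitations of the Proposed Study, the Adherence item says: "Our power calculations show adequate power even after realistic amount of non-adherence". No non-adherence rate or dilution factor appears in the power section.

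**The concern.** The power section fixes every input, so a reader should be able to reproduce the table, and cannot. The heading HR adds doubt. Under Definition of Main Endpoints, placental infection is a single smear status at delivery, and under Data Analysis it is compared by a chi-squared test. A hazard ratio and a ratio of proportions give different power at these event rates.

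Placental malaria is the first primary endpoint and the safety endpoint. If the trial shows no difference, readers will ask what difference it could have detected. That needs a table tied to a known test, effect scale and sample size. The adherence sentence matters for the same reason: it assures the reader that a margin is built in.

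**Working it through.** **Inputs.** Two-sided alpha 0.05 (z = 1.960). Evaluable women: 1,500 × 0.90 = 1,350, or 675 per arm. The 1:1 split is an assumption; the protocol has two regimens and states no unequal ratio. Placebo rate p₁ = 0.20, 0.25, 0.30. Active rate p₂ = p₁ × (1 − reduction).

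**Stated test (unpooled variances).** Power = Φ(|p₁ − p₂| / √{[p₁(1 − p₁) + p₂(1 − p₂)]/n} − 1.960).

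For the quoted case, p₁ = 0.20 and p₂ = 0.13: 0.07 / √[(0.1600 + 0.1131)/675] = 0.07/0.02012 = 3.48. Power = Φ(1.52) = 93.6%; the table prints 80%.

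All cells, printed → recomputed (%):

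| Placebo rate | 25% reduction | 30% | 35% | 40% |
|---|---|---|---|---|
| 20% | 48 → 67.8 | 65 → 83.7 | 80 → 93.6 | 90 → 98.1 |
| 25% | 57 → 79.5 | 74 → 92.3 | 87 → 97.9 | 95 → 99.6 |
| 30% | 64 → 88.2 | 80 → 96.8 | 92 → 99.5 | 98 → 99.9 |

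Only the last cell is within 2 points. The largest gap is 24 points (30% rate, 25% reduction). Pooling the variance changes the results by no more than about 0.2 points. Reading the 10% adjustment as 1,500/1.1 (682 per arm) raises them slightly.

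**What would give the printed values?**
- *Stated test, another n.* Solving each cell for n gives 364 to 437 per arm. No single n fits: the best, about 400, still misses by up to 3.7 points.
- *HR scale, smaller n.* Put p₂ = 1 − (1 − p₁)^HR. For 20% and HR 0.65, p₂ = 1 − 0.80^0.65 = 0.135. At 500 per arm the rows are 47.8/64.3/78.9/89.6, 56.8/74.1/87.2/95.1 and 64.8/81.6/92.5/97.8. All 12 cells are within 1.6 points of print.
- *HR scale, 675 per arm, effect diluted by 13%.* Replace 1 − HR by 0.87 × (1 − HR). The rows are 47.8/64.0/78.4/89.0, 56.8/73.8/86.8/94.7 and 64.7/81.3/92.2/97.5. Again all 12 cells are within 1.6 points.

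The last two explanations cannot be told apart from the table.

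**Detectable effect.** Under the stated test at 675 per arm, 80% power is reached at risk ratios of about 0.71, 0.75 and 0.78 for placebo rates of 20, 25 and 30%, with full adherence.

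**Continuous table.** Power = Φ(difference / (SD × √(2/675)) − 1.960); the smallest effect for 80% power is (1.960 + 0.842) × SD × √(2/675).
- Density (mean 9,000, SD 5,000): standard error 272.2. Smallest effect 762/9,000 = 8.5% (printed 8.5%). Power at 5% and 10%: 38.0% and 91.1% (printed 38% and 91%).
- Hemoglobin (11.4, SD 3.8): standard error 0.207. Smallest effect 5.1% (printed 5.0%). Power at 5%: 78.7% (printed 79%).
- Birth weight (3,083, SD 400): standard error 21.8. Smallest effect 61/3,083 = 2.0% (printed 2.0%).

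This table reproduces with loss to follow-up alone and leaves no room for non-adherence.

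**Illustration.** The protocol gives no non-adherence rate, so 10% and 20% dilution of the effect are assumptions:

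| Outcome and effect | No dilution | 10% | 20% |
|---|---|---|---|
| Density, 8.5% | 80.3% | 71.6% | 61.4% |
| Hemoglobin, 5% | 78.7% | 69.9% | 59.7% |
| Birth weight, 2% | 80.8% | 72.2% | 62.0% |

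**The case against.** The strongest reply is that the malaria table errs on the safe side. Its powers are below what the stated inputs give, so the sentence on a 35% effect at a 20% rate is true, with room to spare, and the sentences on the 25% and 30% rates also hold. Correcting the table raises every cell and changes neither the sample size nor the design. All of this stands. It limits the consequence but does not make the table follow from its specification.

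A reader might go further and infer that no table contains any allowance for non-adherence. The documents do not show that for malaria. The printed values lie on the side where an allowance would put them, and about 13% dilution on an HR scale reproduces them. An undisclosed allowance cannot be excluded there. For the same reason it cannot be said that the table must belong to another trial size.

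A reader might also infer that the inputs themselves are too favourable. Three arguments suggest themselves, and none holds.
- *Retention* ("we are able to achieve follow-up rates of 85-95" per cent): a 10% loss is 90% follow-up, the middle of that range, and the Follow up Schedule section reports more than 95% by six weeks postpartum in similar studies.
- *Home births* ("94.5% of women delivered at a study hospital, while 5.5% delivered at home"): taken with 95% follow-up, 1,500 × 0.95 × 0.945 = 1,347, almost exactly the 1,350 assumed.
- *Placebo rate*: one Kenyan study gives smear-based placental rates of 22% in primigravidae and 14% in secundigravidae ("The corresponding numbers for secundigravidae were 18%, 14% and 54" per cent), about 18% at an equal mix. But the reviews that the power section cites give 26% for placental malaria and a median of 27.8% for maternal infection. A range of 20 to 30% is a documented choice.

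Finally, the dilution rates above are assumed. They show sensitivity and do not prove that actual power will be that low.

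**Conclusion.** The point holds in two limited parts.

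First, the malaria table is wrong as specified: 11 of 12 cells are too low by more than 2 points and the headings name the wrong effect measure. This rests on 1:1 allocation and on reading the 10% adjustment as 675 evaluable per arm. The direction is conservative, so the stated conclusion of good power survives.

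Second, the adherence claim has no stated rate behind it. It is unsupported for density, hemoglobin and birth weight, whose table contains no allowance. For malaria it is neither supported nor disproved. If dilution was used for malaria only, the two tables rest on different assumptions and the protocol does not say so. Here the error flatters the trial: hemoglobin starts at 79% for a 5% effect, so any non-adherence lowers it further below 80%.

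**What to change.** 1. Recompute the malaria table with the stated test at 675 per arm: 68/84/94/98 at 20%, 80/92/98/99.6 at 25%, 88/97/99.5/99.9 at 30%. Head the columns risk ratio. Restate the detectable effect as a risk ratio of about 0.71, 0.75 and 0.78 for 80% power with full adherence. Alternatively, keep the printed table and disclose the effect scale, number per arm and any dilution behind it.
2. Either state a non-adherence rate, with its justification, and carry it through both tables, or delete the sentence in the Adherence limitation.

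The cost is one recomputed table and a few lines of protocol text. Enrollment, procedures and the analysis do not change. The malaria figures rise under the stated test; any figures with a non-adherence allowance will be lower than those without it.
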